MDRD	Modification of Diet in Renal Disease

Abbreviation	Definition
MR	Mineralocorticoid receptor
MRA	Mineralocorticoid receptor antagonist
NF	National Formulary
NT-proBNP	N-terminal of the prohormone brain natriuretic peptide
PD	Pharmacodynamic
PK	Pharmacokinetic(s)
PPK	Population pharmacokinetic(s)
QD	Once daily
QTcF	QT interval corrected using Fridericia's formula
SAE	Serious adverse event
SBP	Systolic blood pressure
TEAE	Treatment-emergent adverse event
UACR	Urine albumin-to-creatinine ratio
ULN	Upper limit of normal
USP	United States Pharmacopeia
WOCBP	Women of childbearing potential

1 INTRODUCTION AND BACKGROUND INFORMATION

High blood pressure and hypertensive kidney damage are the leading cause of morbidity and mortality in the United States.¹ Although considerable progress has been made in the treatment of hypertension and prevention of progression of renal insufficiency, the development of new therapy remains critical. Mineralocorticoid receptor (MR), a member of the steroid receptor family, has been shown to have a major pathophysiological role in the progression of kidney diseases, and the inhibition of MR signaling considerably reduces proteinuria in patients with chronic kidney disease (CKD).^{1,2,3}

Eplerenone is a highly selective aldosterone blocker developed for the treatment of hypertension and heart failure. However, MR antagonism with eplerenone causes a dose-dependent increase in serum potassium concentrations and is contraindicated in hypertensive patients with a creatinine clearance of <50 mL/min. Eplerenone should also be avoided in patients receiving potassium supplements or other potassium-sparing diuretics, such as amiloride and triamterene, particularly in patients with renal insufficiency, diabetes, and microalbuminuria.⁵ In addition, eplerenone causes mild dose-dependent increases in cholesterol, triglycerides, and serum creatinine, and a decrease in serum sodium.⁶ For this reason, a new MR antagonist with an improved efficacy and a low potential for adverse effects in patients with hypertension and moderate-to-severe CKD could potentially address this public health issue and an unmet medical need.

KBP BioSciences Co., Ltd. (hereafter KBP BioSciences) is developing KBP-5074, a new investigational non-steroidal MR antagonist (MRA), for the treatment of hypertension and nephropathy, including diabetic and hypertensive nephropathy. It binds to the MR and blocks the binding of aldosterone, a component of the renin-angiotensin-aldosterone system. Aldosterone binds to MR in both epithelial (eg, kidney) and non-epithelial (eg, heart, blood vessels, and brain) tissues, and increases blood pressure through induction of sodium reabsorption and possibly other mechanisms. Thus, MRAs have the potential to block the deleterious effects of aldosterone on the cardiovascular system.

As a non-steroidal MRA, KBP-5074 has the following potential advantages:

- KBP-5074 selectively binds to recombinant human MRs relative to its binding to recombinant human glucocorticoid receptor, progesterone receptor, and androgen receptor. KBP-5074 has been demonstrated to have better efficacy in lowering blood pressure and renal protection in preclinical disease models than the benchmark compound eplerenone; and
- KBP-5074 demonstrated a favorable safety profile compared to that of eplerenone; with no abnormal levels of potassium, cholesterol, triglycerides, or serum creatinine during the long-term toxicology studies. This suggests that KBP-5074 is potentially a safer and more efficacious MRA.

KBP-5074 is an investigational agent, and limited data regarding its clinical safety profile are available at this time. Because KBP-5074 has the same mechanism of action as eplerenone, common adverse events associated with eplerenone may be relevant: dizziness, diarrhea, coughing, fatigue, and flu-like symptoms.

A battery of pharmacology and toxicology studies including rat and dog acute toxicity studies, rat and dog 4-week and 13-week repeated dose toxicity studies, genotoxicity studies, and safety pharmacology studies were conducted to support the Investigational New Drug application for conducting clinical trials.

Further details regarding the preclinical safety studies of KBP-5074 and clinical development program can be found in the Investigator's Brochure.⁷

An open-label, parallel-group, single ascending dose study in healthy subjects to evaluate the safety, tolerability, and pharmacokinetics (PK) of KBP-5074 following oral administration and with a food-effect panel (Protocol KBP5074-1-001, NCT02228733) has been completed. Single oral doses of KBP-5074 at 0.5, 1.0, 5, 10, and 30 mg in the fasted state and 10 mg in the fed state were safe and well tolerated in healthy male and female subjects (a total of 46 subjects received KBP-5074). There were no drug-related adverse events reported during the study. There were no clinically meaningful trends noted based on safety laboratory assessments, including complete blood count and potassium levels, physical examinations, vital sign measurements, and electrocardiograms (ECGs) during the study. No evidence of bone marrow suppression was observed with increasing drug exposure. Specifically, no clinically meaningful trends of change in the complete blood counts (white blood cell, neutrophils, red blood cell, or platelets) with increasing drug exposure were observed. No gender difference in drug exposure was observed. The time to maximum observed concentration under fasted conditions varied from 4 hours to 7 hours, suggesting relatively fast absorption of KBP-5074 following oral administration under fasted conditions.

An open-label, multiple ascending dose study to evaluate the safety, tolerability, and PK of KBP-5074 in healthy subjects with a separate panel in patients with mild-to-moderate renal impairment (Protocol KBP5074-1-002, NCT02653014) has been completed. Administration of doses of 2.5 mg and 5 mg KBP-5074 once daily (QD) for 14 days in healthy subjects (n = 12), and 0.5 mg and 2.5 mg OD for 56 days in mild-to-moderate CKD patients (n = 14) with proteinuria was safe and well tolerated overall. There was no apparent relationship between doses and the incidence or intensity of treatment-emergent adverse events (TEAEs). Hyperkalemia was observed in the high dose group for both healthy volunteers and mild-to-moderate CKD patients with proteinuria (high risk of hyperkalemia). No hyperkalemia was observed in the 0.5 mg dose group, other than 1 patient with a protocol inclusion violation of excessive serum potassium at baseline (5.1 mmol/L) and a history of acute kidney failure who had a hyperkalemia event (defined as a single observation of potassium > 5.6 mmol/L). All hyperkalemia events (other than in the patient with the protocol violation) were resolved without treatment. A clinically meaningful reduction of urine albumin-to-creatinine ratio (UACR) was observed in both treatment groups in Part 2 of the study. An apparent trend for clinically meaningful reduction of blood pressure was also observed. especially for patients with elevated blood pressure and renal impairment in Part 2 of the study.

A Phase 1, open-label study in hemodialysis (HD) and non-HD patients with severe CKD to evaluate safety, tolerability, and PK of KBP-5074 following oral administration (Protocol KBP5074-1-003, NCT02837237) has been completed. Administration of a single dose of 0.5 mg KBP-5074 in HD patients (n=6) and non-HD patients (n=5) was safe and well tolerated overall. No severe TEAEs, serious adverse events (SAEs), deaths, or study discontinuations due to TEAEs occurred during the study.

A Phase 1, open-label, partial crossover, single-dose study to evaluate the PK, dose proportionality, and safety/tolerability of tablet versus capsule formulations of KBP-5074 in healthy subjects (Protocol KBP5074-1-004, NCT03340753) has been completed. The study was designed to evaluate the PK of a new tablet formulation versus that of the current capsule formulation and help determine dose selection in future studies. Twenty healthy subjects were allocated 4:1 to either the crossover study groups (Cohort 1, 16 subjects) or to the 0.25-mg tablet

single-dose treatment group (Cohort 2, 4 subjects). Subjects allocated to Cohort 1 were randomized 1:1 to 0.5 mg tablet/capsule (8 subjects) or 1.0 mg tablet/capsule (8 subjects). Within Cohort 1, subjects were further randomized to receive a single dose of KBP-5074 (0.5 mg or 1.0 mg) in either capsule or tablet formulation in a 2-period crossover design that was separated by a 2-week washout period and concluded with a 2-week follow-up period. Subjects allocated to Cohort 2 received a single dose of 0.25 mg in tablet formulation only. Cohort 2 provided additional data for the evaluation of dose exposure for the tablet formulation. The bioavailability of KBP-5074 tablet relative to KBP-5074 capsule was slightly higher: approximately 5% to 10% higher in area under the plasma concentration versus time curves (AUCs) and 15% to 20% higher in the maximum observed plasma concentration (C_{max}). Dose proportionality of KBP-5074 tablet in the range of 0.25 mg to 1.0 mg was demonstrated based on Hummel Criteria; dose proportionality of KBP-5074 tablet in the range of 0.25 mg to 1.0 mg was not demonstrated but was close to dose proportionality according to Smith Criteria. Administration of KBP-5074 0.25 mg, 0.5 mg, and 1.0 mg tablet formulations, and 0.5 mg and 1.0 mg capsule formulations was generally safe and well tolerated, and the incidence of TEAEs was similar among treatments.

The current study (Protocol KBP5074-2-001) is a randomized, double-blind, placebo-controlled, multi-center, Phase 2 study to assess the efficacy, safety, and PK of KBP-5074 0.25 mg QD and KBP-5074 0.5 mg QD versus placebo in patients with moderate-to-severe CKD (as defined by estimated glomerular filtration rate [eGFR] \geq 15 and \leq 44 mL/min/1.73 m², based on the isotope dilution mass spectrometry traceable Modification of Diet in Renal Disease [MDRD] equation version 4⁸) and uncontrolled hypertension (Grade 1 to 2 systolic hypertension – European Society of Cardiology [ESC]/European Society of Hypertension [ESH]).

2 STUDY OBJECTIVES

2.1 Primary Objective

The primary objective of this study is to evaluate the efficacy of KBP-5074 in patients with moderate-to-severe CKD on uncontrolled hypertension (eg, Grade 1 to 2 systolic hypertension – ESC/ESH) as determined by change in trough-cuff seated systolic blood pressure (SBP) from baseline to Day 84.

2.2 Secondary Objectives

The secondary objectives of this study are the following:

- To evaluate the change in trough-cuff seated diastolic blood pressure (DBP) from baseline to Day 84;
- To evaluate the change in 24-hour mean, daytime mean, nighttime mean, morning mean, last 6 hours of the dosing interval mean, SBP, DBP, mean arterial pressure (MAP), and heart rate (HR) from baseline to Day 84 in a subset of up to 40 patients per treatment group as measured by 24-hour ambulatory blood pressure monitoring (ABPM);
- To evaluate the change and percent change in UACR from baseline to Day 84 (for patients with albuminuria [defined as UACR > 300 mg/g] or microalbuminuria [defined as UACR in the range of 30 mg/g to 300 mg/g]);
- To evaluate the change in serum aldosterone and plasma renin levels from baseline to Day 84;
- To evaluate the incidence of hyperkalemia (defined as serum potassium ≥ 5.6 mmol/L), incidence of severe hyperkalemia (defined as serum potassium ≥ 6.0 mmol/L), and incidence of patients with serum potassium > 5.0 mmol/L;
- To evaluate the change in serum potassium levels from baseline to Day 84;
- To evaluate the changes in eGFR and creatinine levels > 30% throughout the study period; and
- To evaluate population PK (PPK) of KBP-5074.

3 STUDY DESCRIPTION

3.1 Summary of Study Design

This is a Phase 2, randomized, double-blind, placebo-controlled, multi-center study to assess the efficacy, safety, and PK of KBP-5074 in patients with moderate-to-severe CKD and uncontrolled hypertension (Grade 1 to 2 systolic hypertension – ESC/ESH).

The study will enroll approximately 240 patients, randomized in a 1:1:1 ratio to 1 of 3 treatment groups (80 patients in each group): KBP-5074 0.25 mg QD, KBP-5074 0.5 mg QD, or placebo QD. Randomization will be stratified to balance enrollment for key variables that may influence safety and/or efficacy evaluations, including eGFR (\geq 30 versus < 30 mL/min/1.73 m²) and SBP (\geq 160 versus < 160 mmHg). Approximately 30% of patients enrolled in the study should have eGFR in the range of 15 to 29 mL/min/1.73 m². The study will be approximately 5 months in duration with 84 days of double-blind treatment.

The study will consist of up to a 4-week screening period, 2-week open-label (placebo) run-in period, 84-day double-blind treatment period, and a 4-week post-treatment safety follow-up period.

Plasma samples for PK analysis will be collected from all patients. A total of 4 PK samples will be collected from each patient, including at Day 1 (prior to discharge), Day 14 pre-dose, Day 28 pre-dose, and the End of Study Visit (Day 112)/Early Termination Visit. The pre-dose samples assume that patients will be dosed in the unit on the days above. If patients are not dosed in the unit on those days, a PK sample will be collected during each of these visits and the date and time of the last dose will be recorded.

Safety will be assessed systematically, and an independent data monitoring committee (IDMC) will perform cumulative reviews of safety data at regular intervals during the study.

Serum potassium levels, serum creatinine, and blood pressure will be closely monitored throughout the study and clinically significant changes will be reported as adverse events of special interest.

At Screening and the end of the placebo run-in period (Visit 3), patients must have uncontrolled hypertension (Grade 1 to 2 systolic hypertension – ESC/ESH), defined as resting trough-cuff seated SBP \geq 140 and \leq 179 mmHg, based on the mean of at least 2 current consecutive blood pressure readings in the clinic and a serum potassium \leq 4.8 mmol/L at Screening and the end of the placebo run-in period (Visit 3), and a mean (Visit 1 and Visit 3) eGFR \geq 15 and \leq 44 mL/min/1.73 m².

In all cases, dose and frequency of concurrent antihypertensive medications are expected to be maintained without dose adjustment for 30 days prior to randomization in order to ensure that blood pressure is stable. In general, patients should not add or adjust dose and/or types of the antihypertensive medications they are receiving during the screening period and throughout the duration of the study (unless they develop symptomatic hypotension). The dose of diuretic may be adjusted based on developing or resolved edema, weight gain or loss, or pulmonary congestion.

Patients will be advised to maintain their normal diet and avoid unhealthy levels of alcohol use or potassium-rich foods/drinks during the study period. No potassium supplements are permitted, unless clinically indicated to treat hypokalemia on an emergent basis until serum potassium values

are within the normal range. The use of potassium-sparing diuretics is not permitted within 3 months prior to Screening until the end of study assessments. Intermitted or chronic use of potassium-binding drugs is not permitted for 3 months prior to Screening until the end of study assessments.

After completion of the screening period and the qualifying Screening Visit, patients who meet all eligibility criteria (except those criteria scheduled to be assessed after the Screening Visit), will enter the 2-week, open-label (placebo) run-in period. At the end of the run-in period (Visit 3), patients will be reassessed for eligibility, including persistence of uncontrolled hypertension and compliance with open-label placebo received during the run-in period and current antihypertensive medication. If a patient's compliance is < 80% or > 120%, the patient will not be eligible for the study, and no further visits will be performed.

[figure not shown]
If a patient is found to be ineligible during Screening, a single rescreening is allowed if the Investigator believes that the patient's condition has changed, and the patient may be eligible before the rescreening tests. Please note that a new patient number should be assigned to any rescreened patient, and all of the procedures defined in the protocol for the Screening Visit and during the run-in period must be repeated.

Patients who meet all eligibility criteria at Visit 4/Day 1 will be randomized (stratified based on eGFR \geq 30 versus < 30 mL/min/1.73 m² and SBP \geq 160 versus < 160 mmHg) into the study on Day 1. All randomized patients will receive double-blind treatment for 84 days. Patients will be followed for 4 weeks for safety assessments after the last dose of study drug. Antihypertensive therapy may be modified if necessary during the safety assessment, following withdrawal of the study drug to maintain blood pressure control.

A subset of up to 40 patients per treatment group who agree to participate in 24-hour ABPM and still meet eligibility criteria at the end of the run-in period (Visit 3) will undergo 24-hour ABPM on Day -1, Day 40, and Day 82.

A study schematic is presented in Figure 1.

Figure 1. Study Schematic

EOS = end of study; QD = Once daily.

3.2 Risk Management

3.2.1 Independent Data Monitoring Committee

An IDMC will be established to monitor this study. The IDMC will independently review the safety data and determine if it is safe to continue the study according to the protocol. An IDMC charter will be developed accordingly.

The following will be closely monitored throughout the study:

- Serum potassium levels (see Section 8.12 for details),
- Serum creatinine (see Section 8.13 for details), and
- Blood pressure (see Section 8.14 for details).

3.3 Study Indication

Uncontrolled hypertension in patients with moderate-to-severe CKD.

4 SELECTION AND WITHDRAWAL OF PATIENTS

4.1 Inclusion Criteria

Patients who meet all of the following criteria will be eligible to participate in the study:

- 1. Male or female, between 18 and 85 years of age, inclusive. The lower age limit may be higher if it is legally required in the participating country;
- 2. Body mass index between 19 and 45 kg/m², inclusive;
- 3. Stage 3B/4 CKD (defined as eGFR ≥ 15 and ≤ 44 mL/min/1.73 m², based on the isotope dilution mass spectrometry traceable MDRD equation version 4, according to central laboratory results at Screening [single retest is allowed]);
- 4. Uncontrolled hypertension (Grade 1 to 2 systolic hypertension ESC/ESH), defined as:
 - Resting trough-cuff seated SBP ≥ 140 and ≤ 179 mmHg based on the mean of at least 2 current consecutive clinic blood pressure readings at Screening and at the end of the placebo run-in period (Visit 3); AND
 - Currently on 2 or more antihypertensive medications, which have been titrated upward as tolerated to recommended hypertension target doses (such as diuretics [except for potassium-sparing diuretics], renin-angiotensin system blockers, and/or calcium channel blockers. One of the antihypertensive medications must be high ceiling diuretic (loop or thiazide-like), unless there is a documented intolerance or contraindication to diuretic therapy. The doses of the antihypertensive medications should be stable without any dose adjustment during the 30 days prior to randomization; OR
 - o Patients with uncontrolled hypertension and moderate-to-severe CKD with documented history of intolerance to multiple antihypertensive medications on fewer than 2 antihypertensive medications;
- 5. Serum potassium ≤ 4.8 mmol/L at both Screening and the end of the placebo run-in period. A single retest is allowed to exclude laboratory error or hemolyzed samples;
- 6. Women of childbearing potential (WOCBP) must agree to use 2 medically accepted, effective methods of birth control during the study and for 90 days after the end of the study. Adequate methods of contraception are defined as those that result in a low failure rate (< 1% per year) when used consistently and correctly. Such methods include the use of oral contraceptives, other hormonal contraceptives (vaginal products, skin patches, or implanted or injectable products), or mechanical products (such as an intrauterine diaphragm, condoms, or spermicides);
 - WOCBP are defined as women who are not surgically or chemically sterilized, including hysterectomy or bilateral oophorectomy (tubal ligation is not acceptable), and who are between menarche and 1-year post-menopause; and
 - O Post-menopausal is defined as amenorrheic for at least 1 year, AND if aged under 60 years, have a serum follicle-stimulating hormone (FSH) level > 20 mIU/L. Women who are taking hormone replacement therapy (HRT) do not have to have FSH assessments, but the amenorrhea (before starting HRT) must have been naturally (spontaneously) occurring and

have been accompanied by an appropriate clinical profile (eg, age appropriate and history of vasomotor symptoms);

- 7. Males with partners who are WOCBP must agree to use condoms plus spermicide and their female partner must also be using contraception (eg, hormonal or intra-uterine device). This double contraception must be used from the first dose of study drug until at least 90 days after the last dose of study drug;
- 8. Males must also refrain from donating sperm during the study and for 90 days after the last dose; and
- 9. Capable of understanding the written informed consent, provide signed and witnessed written informed consent before any study-specific procedure, and agree to comply with protocol requirements.

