6.2 Screening Visit (Visit 1)

The following procedures will be performed at Visit 1:

- Obtain informed consent:
- Assess eligibility criteria;
- Record demographics and medical history;
- Perform physical examination;
- Record height and weight;
- Calculate body mass index;
- Contact IRT;
- Perform 12-lead ECG in triplicate (patients should be resting in a supine position for at least 10 minutes prior to assessment);
- Obtain vital signs, including pulse rate, respiratory rate, and oral temperature;
- Obtain blood pressure;
 - Note: Patients must have uncontrolled hypertension, defined as resting trough-cuff seated SBP ≥ 140 and ≤ 179 mmHg, based on the mean of at least 2 current consecutive blood pressure readings in the clinic;
 - o Blood pressures are to be obtained according to the AHA recommendations for accurate blood pressure measurement. Patients should avoid smoking, caffeine, or exercise within 30 minutes before measurement; empty his or her bladder; then sit quietly in a comfortable chair with back support for at least 10 minutes before measurement and remain still during the measurement. The patient's limb should be supported to measure blood pressure to ensure that the blood pressure cuff is at heart level, using the correct cuff size. Do not take the measurement over clothes. Blood pressure measurements should be performed in the same arm throughout the study. Triplicate blood pressure measurements should be taken approximately 2 minutes apart with a validated, oscillometric upper arm blood pressure monitor. Trough cuff SBP and DBP values will be assessed based on the pre-defined blood pressure measurement guideline throughout the study. Pulse will be obtained simultaneously with blood pressure measurements;
- Obtain blood samples for:
 - o HIV, HbsAg, and HCV tests;
 - o Clinical laboratory tests (central laboratory; see Appendix B); and
 - o FSH (post-menopausal women only);

- Obtain urine sample for:
 - o Drug screen;
 - o Urinalysis (central laboratory; see Appendix B); and
 - O UACR:
- Obtain serum sample for potassium (local and central laboratories);
 - Note: Serum potassium should be $\leq 4.8 \text{ mmol/L}$ (local lab) to advance or continue to the placebo run-in Period;
- Obtain serum sample for creatinine (central laboratory);
- Obtain serum sample for pregnancy test (WOCBP only); and
- Record adverse events and concomitant medications.

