6.4.2 Day 1 (Visit 4) \pm 2 Days

This visit is to be scheduled within 4 ± 2 days after the end of the run-in period (Visit 3).

The following procedures will be performed at Visit 4:

- Assess eligibility: Patients must have uncontrolled hypertension, defined as resting trough-cuff seated SBP ≥ 140 and ≤ 179 mmHg, based on the mean of at least 2 current consecutive blood pressure readings in the clinic. Prior to randomization, all patients are to have a serum potassium ≤ 4.8 mmol/L at both Screening and the end of the placebo run-in period; and a mean (Visit 1 and Visit 3) eGFR ≥ 15 and ≤ 44 mL/min/1.73 m².
- Record weight;
- Perform physical examination (pre-dose);
- Perform 12-lead ECG in triplicate (patients should be resting in a supine position for at least 10 minutes prior to assessment);
- Obtain vital signs, including pulse rate, respiratory rate, and oral temperature;
- Obtain blood pressure prior to study drug administration;
 - O Blood pressures are to be obtained according to the AHA recommendations for accurate blood pressure measurement. Patients should avoid smoking, caffeine, or exercise within 30 minutes before measurement; empty his or her bladder; then sit quietly in a comfortable chair with back support for at least 10 minutes before measurement and remain still during the measurement. The patient's limb should be supported to measure blood pressure to ensure that the blood pressure cuff is at heart level, using the correct cuff size. Do not take the measurement over clothes. Blood pressure measurements should be performed in the same arm throughout the study. Triplicate blood pressure measurements should be taken approximately 2 minutes apart with a validated, oscillometric upper arm blood pressure

monitor. Trough cuff SBP and DBP values will be assessed based on the pre-defined blood pressure measurement guideline throughout the study. Pulse will be obtained simultaneously with blood pressure measurements;

- Obtain blood sample for clinical laboratory tests (central laboratory; see Appendix B);
- Obtain urine sample for:
 - o Urinalysis (central laboratory; see Appendix B);
 - o Urine pregnancy test for WOCBP only (pre-dose);
 - o UACR; and
 - o 24-hour urine for UACR;
- Obtain serum sample for potassium (local and central laboratories);
- Obtain serum sample for creatinine (central laboratory);
- Obtain plasma sample for PK from all patients (prior to patient's release from the unit);
- Obtain serum sample for aldosterone;

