APPENDIX B: CLINICAL LABORATORY ANALYTES

Standard Safety Chemistry Panel

Alanine aminotransferase
Albumin
Alkaline phosphatase
Aspartate aminotransferase
Blood urea nitrogen
Chloride
Albumin
Amylase
Bicarbonate
Calcium
Creatine kinase

Chloride Creatine Kinase

Creatinine Estimated glomerular filtration rate¹

Gamma-glutamyl transferase Glucose

Inorganic phosphorus Lactate dehydrogenase

Lipase Potassium
Sodium Total bilirubin
Total protein Uric acid

Calculated by the central laboratory using the Modification of Diet in Renal Disease equation version 4.

Endocrinology

Follicle-stimulating hormone (FSH) for post-menopausal women only¹

Post-menopausal is defined as amenorrheic for at least 1 year AND have a serum FSH level of > 20 mIU/mL.

Hematology

Hematocrit Hemoglobin

Platelets Red blood cell count

White blood cell count and differential

Urinalysis

Bilirubin Blood
Glucose Ketones
Leukocyte esterase Microscopy¹

Nitrite pH

Protein Specific gravity

Urobilinogen

Additional Urinalysis

Urine drug screen

Percent change in urine albumin-to-creatinine ratio (UACR) for spot urine specimen UACR for 24-hour urine specimen

Microscopy is performed only as needed based on positive dipstick test results.

Coagulation

Activated partial thromboplastin time

International normalized ratio

Prothrombin time

Serology

Hepatitis B surface antigen

Human immunodeficiency virus

Hepatitis C virus

Biomarkers

Aldosterone Renin

Serum/plasma samples taken during the study will be stored at a central laboratory for determination of various additional biomarkers, including but not limited to galectin-3, N-terminal of the prohormone brain natriuretic peptide, interleukin-6, collagen biomarkers, and C-reactive protein. The panel of biomarkers and time points for analysis will be determined prior to the database lock.

Pregnancy Test

Serum/urine pregnancy tests will be administered to all women patients of childbearing potential.

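### Inclusion 6 and Appendix B define post-menopausal status by FSH limits that differ 1000-fold and by different age and HRT conditions, so the contraception and pregnancy-test duties of some women under 60 depend on which text is followed

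*Combined protocol and SAP*

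**What the plan says.** Section 4.1, inclusion 6, builds the definition in steps. It begins "Post-menopausal is defined as amenorrheic for at least 1 year, AND if aged under 60 years" and goes on to require that such a woman "have a serum follicle-stimulating hormone (FSH) level > 20 mIU/L". It then adds an exemption: "Women who are taking hormone replacement therapy (HRT) do not have to have FSH assessments". For these women it asks instead that the amenorrhea before HRT arose naturally and fitted the clinical picture.

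The laboratory list gives a second definition, as a note to the FSH entry under Endocrinology in Appendix B: "Post-menopausal is defined as amenorrheic for at least 1 year AND have a serum FSH level of > 20 mIU/mL". It mentions neither age nor HRT.

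The definition has consequences because WOCBP are women not sterilized "and who are between menarche and 1-year post-menopause". Inclusion 6 places the contraception duty on them: "Women of childbearing potential (WOCBP) must agree to use 2 medically accepted, effective methods of birth control". The pregnancy tests at Screening (Section 6.2), before dosing on Day 1 (6.4.2), at End of Study (6.5) and at Early Termination (6.6) are likewise for WOCBP only. FSH is drawn once, at Screening, from post-menopausal women (Section 6.2; Appendix A, footnote 18).

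**The concern.** Both definitions are current protocol text, and they cannot both be applied. Their unit, age condition and HRT condition all differ. The unit difference matters most, because it moves a decision limit by three orders of magnitude.

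The limit does not decide who may enrol, since post-menopausal women and WOCBP can both take part. It decides which duties apply after enrolment. A woman classed as post-menopausal has no contraception requirement under inclusion 6 and no scheduled pregnancy test at any visit. Exclusion 26 covers only women already known to be pregnant, so it does not replace the tests. Section 8.5 requires a patient who becomes pregnant on study drug to be withdrawn at once, with reporting within 24 hours, so the protocol itself treats the event as serious.

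**Working it through.** The documents derive no figure from this limit, so there is nothing to reproduce. The check is a unit conversion followed by a comparison of the two definitions.

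**Inputs**
- Section 4.1, inclusion 6: FSH > 20 mIU/L, required only under age 60, waived on HRT.
- Appendix B, Endocrinology: FSH > 20 mIU/mL, no age condition, no HRT exemption.
- Both: amenorrhea for at least 1 year.

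**Conversion** (1 mL = 1/1000 L)
- Inclusion 6 limit: 20 mIU/L ÷ 1000 = 0.02 mIU/mL.
- Appendix B limit: 20 mIU/mL × 1000 = 20,000 mIU/L.
- Ratio: 20 ÷ 0.02 = 1000.

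**Classification** of a woman amenorrheic for at least 1 year and not on HRT:

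| Age | FSH (mIU/mL) | Post-menopausal by inclusion 6? | Post-menopausal by Appendix B? |
|---|---|---|---|
| Under 60 | up to 0.02 | No | No |
| Under 60 | above 0.02, up to 20 | Yes | No |
| Under 60 | above 20 | Yes | Yes |
| 60 or over | up to 20 | Yes (no FSH needed) | No |
| 60 or over | above 20 | Yes | Yes |

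Test values of 0.01, 0.02, 0.021, 5, 20 and 20.1 mIU/mL at ages 52, 59, 60 and 65 gave this pattern.

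**Women on HRT.** Inclusion 6 needs no FSH result if the clinical history fits. Appendix B as written still needs FSH above 20 mIU/mL.

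**Direction.** In every disagreeing row of the table, inclusion 6 gives post-menopausal and Appendix B does not. The unit conflict produces the under-60 row. The 60-or-over row comes from the age condition alone; the factor of 1000 plays no part in it.

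**The case against.** The best reply is that this is one lost letter. The number, the comparator and the rest of the unit agree, and Appendix B, where a laboratory would look, prints mIU/mL. Nothing shows that a site or laboratory ever applied 0.02 mIU/mL. A fault in reading the PDF cannot be wholly excluded. The laboratory manual mentioned in Section 8.7 is not available here and may state the reporting unit. All of this is fair, and it limits what can be said about actual misclassification. It does not reconcile two printed limits, nor does it explain the differing age and HRT conditions.

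A reader might also infer more than the documents support:

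- **That the mIU/L limit would screen out almost nobody.** This needs the distribution of FSH in amenorrheic women, which the documents do not give. They show only that values above 0.02 and up to 20 mIU/mL are classified differently.
- **That FSH is the sole safeguard for women under 60.** Both definitions keep the one-year amenorrhea rule, and inclusion 6 sends women on HRT through a clinical-history route instead. FSH is also drawn only from women recorded as post-menopausal, so it appears to confirm a status already presumed.
- **That women of 60 or over are put at risk.** Inclusion 6 asks no FSH of them and Appendix B adds a requirement. That is an inconsistency, but the documents show no resulting harm.

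**Conclusion.** The conflict is real and exact: a factor of 1000 in the FSH limit, with different age and HRT conditions. Its practical consequence is confined to women under 60 who have been amenorrheic for at least a year, are not on HRT, and have FSH above 0.02 and up to 20 mIU/mL. For them, inclusion 6 as written lifts duties that would stay in place under Appendix B. For women of 60 or over and women on HRT, the texts disagree without a demonstrated safety gap.

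This rests on two assumptions: that a woman who meets the post-menopausal definition is treated as not WOCBP, and that a site applies the unit as printed. The documents do not show that anyone was in fact misclassified, and they give no count of women in the affected range.

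The mismatch itself is certain; how often it would matter is unknown. It should be corrected because it governs a safety procedure. Sample size, power and the primary analysis are not affected.

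**What to change.** Reconcile Section 4.1, inclusion 6, and the Endocrinology note in Appendix B to a single definition, with the same unit, limit, age condition and HRT condition in both places. Aligning only the unit and the age condition would leave the HRT conflict standing. Alternatively, state the definition once in Section 4.1 and have Appendix B refer to it. Check that the unit matches the one in which the central laboratory reports FSH, and that the laboratory manual agrees. Which limit and conditions are right is for the sponsor to settle.

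The cost is protocol wording only. Design, visits, sampling, sample size and analysis do not change.
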